Recently developed imaging techniques provide not only an opportunity to estimate and visualise RT-induced damage, but they also offer the opportunity to identify new targets for interventions to prevent or lessen cognitive side-effects. Previous neuroimaging studies only focused on micro-, and macrostructural anatomical changes after RT, including grey¹⁶ and white matter¹⁷ (WM) changes. More recent advanced magnetic resonance imaging (MRI) acquisition and analysis techniques, including diffusion-weighted and functional MRI, are nowadays available. They allow us to probe the underlying structural and functional brain network (i.e. "connectome"), respectively. These techniques might be more sensitive to detect possible therapy-induced structural and functional changes in the brain topology, which could relate to cognitive deficits. Furthermore, cognitive impairment may be driven by damage to specific fibre tracts associated with cognitive assessments, which can be modelled based on diffusion-weighted MRI tractography¹⁸.

The proposed observational cohort study will combine the above-mentioned MR imaging techniques together with elaborate neuropsychological assessments and RT dosimetry in 120

patients who will be examined baseline (before RT) and followed longitudinally after RT. By doing so, we hope to uncover vulnerable brain regions and detect early imaging changes to identify patients at risk. Since neurotoxicity is a complex multifactorial process, the best way to combine these data and make predictions about RT-induced effects is to build so-called normal tissue complication probability (NTCP) models. These mathematical models allow us to estimate the risk of a particular side effect in a structured and validated way for every individual patient. This will enable us to simulate the patient's toxicity risks to spare neurocognitive function in daily life. A previous effect has been conducted by Gondi in 2012, but included a limited number of patients and this model has not been validated to date¹⁹.

In this exploratory prospective study, we thus aim to provide the clinical, radiological and dosimetric data to build a validated NTCP model for neurocognitive decline, which is currently lacking.

3. Trial objectives and Design

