7.1 Sample size

Study subjects will be recruited from the radiation-oncology center of three centers: UZ Leuven, UZ Gent and Iridium Kankernetwerk Antwerpen. From a pragmatic perspective, we estimate to recruit 12-15 patients yearly in each of the three centers, resulting in 120 patients in three years in total.

Cognitive impairment has been reported in primary brain tumour patients and is roughly estimated to be present in about half of patients³⁹⁻⁴⁰. Although limited (good quality) evidence exists for our

type of study, power calculations were performed based on the two most extreme studies (i.e. one showing minimal amount of cognitive impairment⁴¹ and one showing maximal amount of cognitive impairment⁴². In both studies cognitive performance is assessed at baseline and about 12 months after radiotherapy in primary brain tumours. In the study by Moretti et al⁴², we used the cognitive outcome results of patients 9-12 months after radiotherapy (45-60 Gy), since the studied population will receive radiotherapy doses within this range. For power calculations, we used the performance on the digit span forward (processing speed) since the prevalence of impairment on this test was low (<20%). Based on these studies, effect sizes of d= 0,368 and d= 1,271 were found with a power of 0,800 and 0,868 respectively. This power would be 0,979 and 1,000 in our specific explorative study, in case of 120 inclusions. In order to detect this difference after 12 months with a power of 0.800 and a two-sided significance level α =0,05, the total required sample size would thus range between 8-60 patients. Power calculations were performed using Gpower 3.1⁴³.

Sample size calculation for the prediction models was performed using a recently developed software package⁴⁴. Since the event rate of cognitive impairment is unclear, we performed power calculations for the lowest and highest event rate, i.e. 0,2-0,5 (see above). When considering 4 candidate predictors and rMSPE of 0,1, the required sample sizes ranges between 90 and 120 patients respectively. Therefore, including 120 patients will allow building a sufficiently complex prediction model combining four dosimetric and/or clinical features.

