a multivariable prediction model (logistic regression model with LASSO regularization) will be built with only the clinical variables using a forward stepwise procedure with p = 0.05 (deviance criterion) as critical p-value to stay in the model. Afterwards, the clinical prediction model will be extended by a stepwise addition of dosimetric variables which are ranked in the univariable analysis. In this multivariable prediction model (LASSO), a maximum of 4 variables will be included in each model. Finally, we will test in all models whether proton beam therapy (PBT) itself has an additional independent impact on the outcome risk apart from the already selected dose metrics. If that is the case, this will be investigated further by linear energy transfer (LET) and relative biological effectiveness (RBE) weighted PBT dose maps instead of the standard (RBE=1.1) PBT dose maps. The discriminative ability of the prediction models will be quantified using the AUC and compared between nested models using the likelihood ratio test. To obtain stable prediction models, all modelling steps will be repeated in a 100 times repeated 5-fold cross-validation process. The most frequently obtained models will be selected. Final model coefficients will be determined by fitting these selected models on the complete development dataset. Correction for optimism will be performed using 500 bootstrap samples.

In a second effort, relevant 3D clusters of brain voxels resulting from the brain damage susceptibility heat maps will be included in the modelling. Dose to these brain areas will be used as alternative dosimetric input parameters and the resulting model's performance will be compared to that obtained in the first step. The final NTCP model parameters will be calculated for the whole dataset of patients and per institution in order to detect potential heterogeneity.

Internal validation of the model will be performed using bootstrapping. After external validation, the final NTCP models could possibly be included in decision support software. In case of conflicting neurotoxicity constraints, several 'optimal' solutions to the planning problem (prioritizing one or another brain region) might indeed be possible. This will facilitate plan comparisons and informed decisions on the optimal treatment plan in future patients.

8. Quality assurance

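### AUC is the only performance measure named for models meant to give individual risks, and the plan leaves open whether the final fit is penalised and whether the bootstrap correction covers calibration and repeats variable selection

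*Protocol*

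**What the plan says.** The purpose is individual risk. Section 2 (Background and rationale) describes the purpose of NTCP modelling as follows: "These mathematical models allow us to estimate the risk of a particular side effect in a structured and validated way for every individual patient". Section 3.1 wants a tool for choosing the treatment modality of each patient, and the end of section 7.2.4 foresees help with comparing plans.

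Section 7.1 sizes the prediction models on the error of the predicted probability: "When considering 4 candidate predictors and rMSPE of 0,1, the required sample sizes ranges between 90 and 120 patients respectively".

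Section 7.2.4 describes both multivariable models as LASSO logistic regression. It combines the clinical model with forward selection at p = 0.05 on the deviance and caps each model at four variables. On performance it says: "The discriminative ability of the prediction models will be quantified using the AUC and compared between nested models using the likelihood ratio test". All steps of model building are repeated in 100 rounds of 5-fold cross-validation, and the models found most often are kept. Then: "Final model coefficients will be determined by fitting these selected models on the complete development dataset". The next sentence prescribes an optimism correction with 500 bootstrap samples, without naming the quantity to be corrected. Bootstrap internal validation follows, and external validation is to come before any use in decision software.

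The protocol nowhere mentions a calibration slope, intercept, calibration plot or Brier score.

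**The concern.** A plan comparison rests on the difference between two predicted risks, so the risks must be right in absolute terms. AUC depends only on how patients are ranked and stays the same if every log-odds is doubled or halved. The likelihood ratio test asks whether added variables improve the fit in the development data; it says nothing about the size of predicted risks in new patients. A model could therefore pass every named check and still overstate or understate the gain of one plan over another.

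Three points that decide the calibration of the published model are open: whether the final fit is penalised, what the bootstrap corrects, and whether each bootstrap sample repeats the variable selection. Repetition of all steps is stated for the cross-validation only.

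**Working it through.** **Inputs from the protocol.** n = 120; event rate 0.2 to 0.5, so 120 × 0.2 = 24 to 120 × 0.5 = 60 events; sample size based on 4 candidate predictors and rMSPE 0.1; seven clinical candidates named in section 7.2.4 before any dose metric; entry at p = 0.05; at most 4 variables.

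**Assumptions not in the protocol.** Number of dose candidates, effect sizes and correlations, as given with each simulation.

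**1. The plan's own figure.** In large samples with weak predictors, N ≈ φ(1 − φ)(P + 1)/rMSPE².
- φ = 0.2: 0.16 × 5/0.01 = 80.
- φ = 0.5: 0.25 × 5/0.01 = 125.

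Simulated unpenalised logistic regression with 4 predictors and no selection gives rMSPE 0.100–0.105 at N = 90 (φ = 0.2) and 0.094–0.103 at N = 120 (φ = 0.5). The stated 90 to 120 reproduces, for four predictors fixed in advance.

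**2. The measure used below.** In new patients, fit logit P(event) = a + b × (model's linear predictor). A slope b = 1 is calibrated, b < 1 means risks too extreme, and b > 1 means too moderate. A log-odds difference between two plans is shown 1/b times its true size: 1/0.5 = 2 times at b = 0.5, and 1/1.56 = 0.64 times at b = 1.56.

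**3. Four or 12 candidates.** Three true predictors with log-odds 0.35 or 0.6 per SD, correlation 0.3, 60 runs per cell. The LASSO penalty was chosen by 5-fold cross-validation among penalties leaving at most 4 variables. Runs that selected nothing were dropped, leaving 52 to 60 per cell. Median slopes:

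| Event rate | Candidates | Log-odds per SD | LASSO coefficients kept | Unpenalised refit of the same variables |
|---|---|---|---|---|
| 0.2 | 4 | 0.35 | 0.94 | 0.69 |
| 0.2 | 4 | 0.6 | 1.06 | 0.81 |
| 0.2 | 12 | 0.35 | 1.16 | 0.53 |
| 0.2 | 12 | 0.6 | 1.41 | 0.63 |
| 0.5 | 4 | 0.35 | 0.95 | 0.80 |
| 0.5 | 4 | 0.6 | 1.03 | 0.88 |
| 0.5 | 12 | 0.35 | 1.42 | 0.71 |
| 0.5 | 12 | 0.6 | 1.56 | 0.75 |

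Forward selection with an unpenalised refit gave 0.77–0.86 (4 candidates) and 0.58–0.75 (12). Multiplying that refit by the bootstrap-corrected slope gave 0.89–1.05.

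**4. More candidates.** Seven clinical plus 10 to 20 correlated dose variables, forward entry at p < 0.05, at most 4 variables, unpenalised refit, true AUC about 0.71, 250 development sets per scenario. Median slope was 0.39–0.49 at event rate 0.2 and 0.52–0.58 at 0.5. A repeat with separate code and its own assumed effects (150 runs per cell) gave 0.41–0.46 and 0.50–0.51.

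**5. Would a corrected AUC reveal it?** No. In step 3 the optimism-corrected AUC was 0.63–0.77 against a true 0.63–0.76, while the slopes of the unpenalised refits were well below 1.

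**6. Does the bootstrap need to repeat selection?** With an unpenalised refit (40 runs per cell, assumed effects), the true slope was 0.43–0.59. A bootstrap that held the selected variables fixed estimated 0.94–1.03, so it would report almost no problem. Rerunning the selection gave 0.53–0.65: still somewhat optimistic, but close enough to show the problem.

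**The case against.** The strongest case against has four parts.

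- **The models are labelled LASSO, and nothing says the penalty is dropped.** This stands. A reader might infer that the final fit is unpenalised and that risks will be too extreme; the text does not support that as a certainty. It does not settle calibration either: with 12 candidates, retained LASSO coefficients were too moderate.
- **An optimism correction follows directly after the sentence on the final coefficients, with bootstrap internal validation and later external validation.** This also stands. A reader might infer that nothing in the plan would detect or correct miscalibration; that is not supported. But the correction names no quantity and does not say that selection is repeated, and step 6 shows that this second point decides whether it works. External validation is left to later work and does not protect the coefficients this study produces.
- **The AUC sentence covers discrimination only, and calibration may be in an analysis plan that is not shown.** Silence on calibration alone would indeed be no finding. However, the protocol itself fixes the entry criterion, the variable cap, the cross-validation repeats, the number of bootstrap samples and the performance measure. That set, as fixed, does not match the stated use or the rMSPE basis of the sample size.
- **The simulations are not the full procedure of the protocol.** Correct. They omit the 100-fold repetition and the choice of the most frequent model, and the sizes depend on assumed candidates and effects. They show direction and plausible range, not a forecast.

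**Conclusion.** The point holds in conditional form. The plan names AUC as the only performance measure for models whose purpose is absolute risk, and leaves the penalty in the final fit and the scope of the optimism correction open.

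If the refit is unpenalised and the bootstrap corrects only the AUC, or holds the selected variables fixed, predicted risks would be too extreme: simulated slopes of about 0.4 to 0.9. Log-odds differences between plans would then be overstated by a factor between 1/0.9 = 1.1 and 1/0.4 = 2.5. If LASSO coefficients are kept, slopes were near 1 with 4 candidates and 1.16 to 1.56 with 12, so differences may be understated. AUC reveals neither.

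These sizes rest on 120 analysable patients, event rates of 0.2 to 0.5, assumed numbers of candidates and effects, and 40 to 250 runs per cell. That calibration needs to be measured does not depend on them. This is a cheap improvement, not a flaw that invalidates the design.

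**What to change.** Amend section 7.2.4, or the analysis plan, in three places:

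1. In each of the 500 planned bootstrap samples, rerun the whole procedure: univariable ranking, correlation filter, transformations, selection and, if used, choice of the penalty.
2. Beside the AUC, report the optimism-corrected calibration intercept and slope, a calibration plot, and a Brier score or rMSPE.
3. State the final fit: either keep the penalised coefficients, or use an unpenalised refit with coefficients multiplied by the corrected slope and the intercept re-estimated.

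The cost is a few lines of text and more computing time; no new data are needed. Published effects will be somewhat smaller if shrinkage is applied.

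### The likelihood ratio test for the added value of dose is applied in the same patients whose outcomes selected the dose variables, so its p-value is invalid; any bias in the voxel-cluster comparison is conditional

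*Protocol*

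**What the plan says.** Section 7.2.4 of the protocol sets out two modelling efforts for each of five cognitive domains.

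In the first effort, clinical variables are ranked by univariable AUC against the endpoint. A clinical LASSO logistic model is built "using a forward stepwise procedure with p = 0.05 (deviance criterion) as critical p-value to stay in the model". That model is then "extended by a stepwise addition of dosimetric variables which are ranked in the univariable analysis", up to four variables in all. Discrimination is measured by AUC and "compared between nested models using the likelihood ratio test".

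The section also plans 5-fold cross-validation, repeated 100 times, covering every modelling step. Its stated use is to find the models obtained most often, which are then refitted on the complete dataset. Optimism is corrected with 500 bootstraps.

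In the second effort, "relevant 3D clusters of brain voxels resulting from the brain damage susceptibility heat maps will be included in the modelling", and the resulting model's "performance will be compared to that obtained in the first step". The protocol does not say which data or endpoint the heat maps are built on, or which performance measure is compared.

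**The concern.** Whether dosimetry adds to clinical information is central to the primary objective, an NTCP model. The likelihood ratio test is the only formal test the section names for it. A chi-square reference assumes that the added variable was chosen without looking at the outcome. Here it is the variable that looked best on that outcome among an unstated number of dose metrics, and it is tested in the same patients. Its test statistic then behaves like a maximum over many candidates, and the test rejects too often when dose has no effect.

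Two further faults need no simulation. A LASSO fit does not maximise the ordinary likelihood, so twice the log-likelihood difference has no standard chi-square reference. And the test compares model fit, although the sentence presents it as a comparison of discrimination.

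The second effort raises a related question. If the clusters were chosen on the same patients' cognitive outcomes and then treated as given, resampling would not see that selection, and the comparison with the atlas model would favour the clusters.

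**Working it through.** **Inputs from the protocol.** N = 120 and a model of up to four features (Section 7.1: "including 120 patients will allow building a sufficiently complex prediction model combining four dosimetric and/or clinical features"); event rate 0.2 to 0.5 (Section 7.1); ranking, stepwise addition and likelihood ratio test (Section 7.2.4).

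**Assumptions.** The protocol gives neither the number K of dose metrics nor their pairwise correlation r, so K = 5, 10, 20, 40 and r = 0, 0.5, 0.8 were tried. The AUC ranking and the 0.05 entry rule, stated for clinical variables, were assumed to apply to dose as well. Unpenalised logistic fits stand in for LASSO. There is one true clinical predictor, independent of dose.

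**The plan's own figure.** The protocol gives no error rate for this test, so the benchmark is the nominal 0.05. Its model sample size ("When considering 4 candidate predictors and rMSPE of 0,1, the required sample sizes ranges between 90 and 120 patients respectively") counts four candidates, whereas Section 7.2.4 lists seven clinical variables before any dose metric. That calculation was not re-derived and does not bear on this point.

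**Step 1: the test with a variable named in advance.** The statistic is 2(l1 − l0), with l0 and l1 the log-likelihoods without and with dose, referred to chi-square on 1 degree of freedom. Over 24 settings of 1,000 runs with no dose effect, a prespecified metric gave rejection rates of 0.035-0.069 (mean 1.231/24 = 0.051). The simulation is therefore calibrated.

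**Step 2: the test after selection.** For K independent metrics, the chance that at least one passes is 1 − 0.95^K: 0.226 (K = 5), 0.401 (10), 0.642 (20), 0.871 (40). The simulated null rejection rates, over both event rates, were:

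| K | top-ranked metric, r = 0.8 | r = 0.5 | r = 0 | stepwise addition, r = 0.8 to 0 |
|---|---|---|---|---|
| 5 | 0.11 | 0.17 | 0.24 | 0.12-0.26 |
| 10 | 0.16 | 0.26-0.28 | 0.37 | 0.18-0.43 |
| 20 | 0.20-0.21 | 0.36-0.39 | 0.55-0.60 | 0.23-0.69 |
| 40 | 0.27-0.28 | 0.50 | 0.78-0.79 | 0.31-0.91 |

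The r = 0 column is close to the formula, and correlation lowers the rate. The mildest setting is still about twice nominal.

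**Step 3: do the planned safeguards repair the test?** Choosing the metric selected most often over repeated 5-fold cross-validation, then testing it on all patients, gave 0.26-0.28 (K = 10, r = 0.5), 0.38-0.40 (K = 20, r = 0.5) and 0.18-0.21 (K = 20, r = 0.8), with 300 runs each. Bootstrap optimism correction adjusts AUC and leaves the p-value as it was.

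**Step 4: do valid alternatives hold their level?** In the same settings, selecting on a random half and testing on the other gave 0.047-0.063. A permutation test repeating the selection gave 0.040-0.070. The second result holds with dose independent of the clinical predictor.

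**Step 5: the second effort under no effect.** A smoothed 24 × 24 dose map was used, comparing the best of 16 atlas regions with a cluster formed by the top 2% of voxels, all chosen on the outcome (150 runs, 60 bootstraps). The gap is the corrected cluster AUC minus the corrected atlas AUC.

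| Event rate, smoothing | Atlas corrected | Cluster, map held fixed | Gap | Cluster, map rebuilt | Gap |
|---|---|---|---|---|---|
| 0.2, 1.5 | 0.545 | 0.737 | 0.192 | 0.596 | 0.051 |
| 0.2, 3 | 0.538 | 0.655 | 0.117 | 0.554 | 0.016 |
| 0.2, 5 | 0.540 | 0.616 | 0.076 | 0.547 | 0.007 |
| 0.5, 1.5 | 0.538 | 0.685 | 0.147 | 0.565 | 0.027 |
| 0.5, 3 | 0.532 | 0.623 | 0.091 | 0.540 | 0.008 |
| 0.5, 5 | 0.525 | 0.586 | 0.061 | 0.528 | 0.003 |

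**The case against.** The best defence is that the section already plans substantial resampling: cross-validation of every modelling step, optimism correction and bootstrap internal validation. Section 2 calls the study exploratory, Section 3.1 foresees later validation trials, and Section 7.2.4 puts external validation before any decision-support use. No success criterion hangs on the likelihood ratio test. All of this stands, and it limits the consequence. It does not rescue the p-value, because none of these steps changes the reference distribution of a test run after selection.

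A reader might also infer that the cluster-versus-atlas comparison is strongly biased as written. The protocol does not support that. No other dataset is named, so building the heat maps on this cohort is a natural reading, but they could reflect dose-related MRI change rather than cognitive impairment. Nothing says that they are built outside the resampling or that uncorrected performance is compared.

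The size of the inflation is also open to challenge. Doses to neighbouring brain structures are likely to be correlated, so the r = 0 column is an upper bound rather than an expectation.

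Finally, combining LASSO with a stepwise p-value rule is unusual, but whether to keep both is a design choice.

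**Conclusion.** The point on the likelihood ratio test holds. The protocol itself fixes a test whose nominal level fails after the selection it prescribes, whose reference distribution does not apply to penalised fits, and which does not compare AUCs. With no dose effect and 120 patients, the false-positive rate for the top-ranked metric is about 0.11-0.24, 0.16-0.37 and 0.20-0.60 with 5, 10 and 20 candidates. These are ranges under assumed numbers and correlations, with unpenalised fits. No single value can be attributed to this trial. The result does not mean that dose has no effect, and it does not carry over in the same way to a variable named in advance.

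For the second effort, the conclusion is conditional. If the maps are derived from these patients' cognitive outcomes and held fixed in the resampling, a spurious AUC gain of about 0.06-0.19 is possible in the simulated setting. If they are rebuilt each time, it is about 0.00-0.05.

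**What to change.** 1. Replace the likelihood ratio test by the paired difference in out-of-fold AUC and deviance between the clinical and clinical-plus-dose pipelines, using the cross-validation already planned. Redo ranking, transformation and selection in every training fold. The 100 × 5 = 500 fold results overlap and should not be treated as independent observations.
2. Run the 500 optimism bootstraps over the whole pipeline, including selection.
3. If a p-value is wanted, use a resampling test that repeats the selection and keeps the relation between dose and the clinical covariates. One option, not simulated here, is to generate outcomes from the clinical-only model with each patient's dose and covariates left as observed. Freely permuting dose vectors is unsuitable: it breaks the link between dose and candidate covariates such as tumour location and treatment modality, and so tests a different null hypothesis.
4. State the data and endpoint from which the heat maps are built. If they use these patients' cognitive outcomes, rebuild maps and clusters in each training fold and bootstrap sample, and compare the two efforts on corrected or out-of-fold performance only.

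The cost is analysis programming and computing time, and the reported AUCs will be lower. No extra patients or data are needed.
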